10.2 Institutional Review Board (IRB) Approval and Consent

It is expected that the IRB will have the proper representation and function in accordance with federally mandated regulations. The IRB should approve the consent form and protocol.

In obtaining and documenting informed consent, the investigator should comply with the applicable regulatory requirement(s), and should adhere to Good Clinical Practice (GCP) and to ethical principles that have their origin in the Declaration of Helsinki.

Before recruitment and enrollment onto this study, the patient will be given a full explanation of the study and will be given the opportunity to review the consent form. Each consent form must include all the relevant elements currently required by the FDA Regulations and local or state regulations. Once this essential information has been provided to the patient and the investigator is assured that the patient understands the implications of participating in the study, the patient will be asked to give consent to participate in the study by signing an IRB-approved consent form.

Prior to a patient's participation in the trial, the written informed consent form should be signed and personally dated by the patient or their legally authorized representative and by the person who conducted the informed consent discussion.

10.3 Required Documentation (for multi-site studies)

Before the study can be initiated at any site, the following documentation must be provided to the Clinical Research Office, Pauline Allen Gill Center for Cancer and Blood Disorders, Children's Medical Center – Dallas.

- A copy of the official IRB approval letter for the protocol and informed consent
- IRB membership list or Federal Wide Assurance letter
- CVs and medical licensure for the principal investigator and any associate investigators who will be involved in the study
- Form FDA 1572 appropriately filled out and signed with appropriate documentation (NOTE: this is required if this institution holds the IND. Otherwise, the affiliate Investigator's signature on the protocol is sufficient to ensure compliance)
- A copy of the IRB-approved consent form
- CAP and CLIA Laboratory certification numbers and institution lab normal values
- Executed clinical research contract
- Site Delegation Log

10.4 Registration Procedures

All patients must be registered with the UT Southwestern Medical Center / Children's Medical Center-Dallas (UTSW/CMC) Research Office before consenting to study participation. Prior to enrollment, eligibility criteria must be confirmed with the Clinical Research Office Study Coordinator at UTSW/CMC. To register a patient, call [contact] Monday through Friday, 8:00AM-4:00PM CST. After hours, [name] (Study Principle Investigator) can be reached through the Children's Medical Center paging operator at [contact].

10.5 Data Management and Monitoring / Auditing

REDCap is the UTSW SCC institutional choice for electronic data capture of case report forms for this and all SCC investigator initiated trials. REDCap will be used for electronic data capture case report forms in accordance with Simmons Cancer Center requirements.

Other institutions participating in this trial as sub-sites will be expected to enter data into REDCap and upload de-identified source materials as instructed by the study team to facilitate remote source to case report form verification.

Trial monitoring will be conducted no less than annually and refers to a regular interval review of trial related activity and documentation performed by the DOT, which includes but is not limited to accuracy of case report forms, protocol compliance timelines and accuracy of Velos entries and AE/SAE management and reporting. Documentation of trial monitoring will be maintained along with other protocol related documents and will be reviewed during the internal audit.

The UTSW Simmons Cancer Center (SCC) Data Safety Monitoring Committee (DSMC) is responsible for monitoring data quality and patient safety for all UTSW SCC clinical trials. As part of that responsibility, the DSMC reviews all local serious adverse events and unanticipated problems in real time as they are reported and reviews adverse events on a quarterly basis. The quality assurance activity for Clinical Research Office provides periodic auditing of clinical research documents to insure data integrity and regulatory compliance. A copy of the DSMC plan is available upon request.

The SCC DSMC meets quarterly and conducts annual comprehensive reviews of ongoing clinical trials, for which it serves as the DSMC of record. The QAC works as part of the DSMC to conduct regular audits based on the level of risk. Audit findings are reviewed at the next available DSMC meeting. In this way frequency of DSMC monitoring is dependent

upon the level of risk. Risk level is determined by the DSMC Chairman and a number of factors such as the phase of the study, the type of investigational agent, device or intervention being studied, and monitoring required to ensure the safety of study subjects based on the associated risks of the study. Protocol specific DSMC plans must be consistent with these principles.

10.6 Adherence to the Protocol

Except for an emergency situation in which proper care for the protection, safety, and well-being of the study patient requires alternative treatment, the study shall be conducted exactly as described in the approved protocol.

10.6.1 Emergency Modifications

Investigators may implement a deviation from, or a change of, the protocol to eliminate an immediate hazard(s) to trial subjects without prior IRB approval.

For any such emergency modification implemented, a IRB modification form must be completed within five (5) business days of making the change.

10.6.2 Other Protocol Deviations/Violations

All other planned deviations from the protocol must have prior approval by the Principal Investigator and the IRB. According to the IRB, a protocol deviation is any unplanned variance from an IRB approved protocol that:

- Is generally noted or recognized after it occurs
- Has no substantive effect on the risks to research participants
- Has no substantive effect on the scientific integrity of the research plan or the value of the data collected
- Did not result from willful or knowing misconduct on the part of the investigator(s).

An unplanned protocol variance is considered a violation if the variance:

- Has harmed or increased the risk of harm to one or more research participants.
- Has damaged the scientific integrity of the data collected for the study.
- Results from willful or knowing misconduct on the part of the investigator(s).
- Demonstrates serious or continuing noncompliance with federal regulations, State laws, or University policies.

If a deviation or violation occurs without prior approval from the Principal Investigator and IRB, please follow the guidelines below:

Protocol Deviations: Personnel will report to any sponsor or data and safety monitoring committee in accordance with their policies. Deviations should be summarized and reported to the IRB at the time of continuing review.

Protocol Violations: Study personnel should report violations within one (1) week of the investigator becoming aware of the event using the same IRB online mechanism used to report Unanticipated Problems.

10.7 Amendments to the Protocol

Should amendments to the protocol be required, the amendments will be originated and documented by the Principal Investigator. It should also be noted that when an amendment to the protocol substantially alters the study design or the potential risk to the patient, a revised consent form might be required.

The written amendment, and if required the amended consent form, must be sent to the IRB for approval prior to implementation.

10.8 Record Retention

Study documentation includes all Case Report Forms, data correction forms or queries, source documents, Sponsor-Investigator correspondence, monitoring logs/letters, and regulatory documents (e.g., protocol and amendments, IRB correspondence and approval, signed patient consent forms).

Source documents include all recordings of observations or notations of clinical activities and all reports and records necessary for the evaluation and reconstruction of the clinical research study.

Government agency regulations and directives require that the study investigator must retain all study documentation pertaining to the conduct of a clinical trial. In the case of a study with a drug seeking regulatory approval and marketing, these documents shall be retained for at least two years after the last approval of marketing application in an International Conference on Harmonization (ICH) region. In all other cases, study documents should be kept on file until three years after the completion and final study report of this investigational study.

10.9 Obligations of Investigators

The Principal Investigator is responsible for the conduct of the clinical trial at the site in accordance with Title 21 of the Code of Federal Regulations and/or the Declaration of Helsinki. The Principal Investigator is responsible for personally overseeing the treatment of all study patients. The Principal Investigator must assure that all study site personnel, including sub-investigators and other study staff members, adhere to the study protocol and all FDA/GCP/NCI regulations and guidelines regarding clinical trials both during and after study completion.

The Principal Investigator at each institution or site will be responsible for assuring that all the required data will be collected and entered onto the Case Report Forms. Periodically, monitoring visits will be conducted and the Principal Investigator will provide access to his/her original records to permit verification of proper entry of data. At the completion of the study, all case report forms will be reviewed by the Principal Investigator and will require his/her final signature to verify the accuracy of the data.

APPENDIX I: Inclusion / Exclusion Checklist

Inclusion Criteria—Complete each box with an “X” to confirm patient meets listed criteria	
	Diagnosis and Age: Ependymoma (WHO grade II) or Anaplastic Ependymoma (WHO grade III) that has relapsed or become refractory to standard therapy. Patients must have had histologic verification of their malignancy at original diagnosis or time of recurrence.
	Age must be \geq 2 years and \leq 21 years of age at study entry.
	Performance status: Lansky \geq 50% for patients \leq 10 years of age or Karnofsky \geq 50% for patients $>$ 10 years of age.
	Adequate bone marrow function as shown by: ANC \geq 1,000/mm ³ , platelets \geq 100,000/mm ³ and hemoglobin $>$ 9.0 g/dL. (These values must be transfusion independent)
	Adequate liver function as shown by: Total serum bilirubin \leq 2.0 mg/dL, ALT and AST \leq 2.5x ULN, INR \leq 2.
	Adequate renal function: serum creatinine \leq 1.5x ULN.
	Fasting serum cholesterol \leq 300 mg/dL OR \leq 7.75 mmol/L AND fasting triglycerides \leq 2.5x ULN (See protocol for exception).
	Signed informed consent obtained prior to any screening procedures
	Patients must have measurable residual disease, defined as tumor that is measurable in two diameters on MRI. Diffuse leptomeningeal disease is not considered measurable.
	Patients must have fully recovered from the acute toxic effects of all prior chemotherapy, immunotherapy, and radiotherapy prior to participating in this trial (see protocol for details).
	All patients must have an MRI of the brain and the complete spine that has measurable tumor (not only diffuse leptomeningeal tumor) within 14 days prior to study enrollment.
	If available, tumor tissue from either initial diagnosis or subsequent surgery will be submitted on Formalin Fixed Paraffin Embedded (FFPE) slides (n = 12) to the Pathology Laboratory at Children’s Medical Center-Dallas for correlative biological studies.
Exclusion Criteria—Complete each box with “No” or “NA”, as appropriate, to confirm eligibility	
	Known intolerance or hypersensitivity to Everolimus or other rapamycin analogs.
	Concomitant use of medications known to have inhibition or induction of CYP3A enzymes (see Table 4-7 and 4-8 for a list of prohibited medications). Note that systemic corticosteroids (e.g., dexamethasone is a CYP3A inducer) are not allowed. Inhaled corticosteroids are allowed.
	Known impairment of gastrointestinal (GI) function or GI disease that may significantly alter the absorption of oral Everolimus.
	Uncontrolled diabetes mellitus as defined by HbA1c $>$ 8% despite adequate therapy. Patients with a known history of impaired fasting glucose or diabetes mellitus (DM) may be included, however blood glucose and antidiabetic treatment must be monitored closely throughout the trial and adjusted as necessary
	Patients who have any severe and/or uncontrolled medical conditions (see protocol)
	Patients with a known history of HIV sero-positivity
	Patients who have received live attenuated vaccines (see protocol for examples) within 1 week of start of Everolimus.
	Patients who have a history of another primary malignancy (see protocol for exceptions).
	Patients with a history of non-compliance to medical regimens or who are considered potentially unreliable or will not be able to complete the entire study.
	Patients who are currently part of or have participated in any clinical investigation with an investigational drug within 1 month prior to dosing.
	Pregnant or nursing (lactating) women.
	Women of child-bearing potential unless they are using highly effective methods of contraception (see protocol for details).
	Sexually active males unless they are using a condom (see protocol for details).
	Hepatitis screening must be completed if necessary (see protocols for details).

I have reviewed the eligibility criteria and confirm the patient is eligible for enrollment.

Physician Signature: _____

Date: _____

APPENDIX II: Time and Events Table

Period/Procedure	Screening	Course 1	Courses 2-24 ¹⁰	End of Treatment Visit ¹³	Long Term Follow Up
Study Day/Visit Day	-14 to 1	Day 14 (+/- 4 days)	Day 1 (+/- 7 days)	Within 30 Days	
Informed Consent	X				
Central Review of Pathology and MRI¹	X				
AE Assessment	X		X	X¹⁴	
Concomitant Medications	X		X	X¹⁴	
Drug Accountability			X	X	
Clinical procedures					
Physical Exam	X		X	X	
Vital Signs	X		X	X	
Medical History	X				
Performance Status	X		X	X	
Neurologic Exam	X		X	X	
Pulse Oximetry²	X		X		
Laboratory procedures					
CBC w/ Diff³	X		X	X	
Blood Chemistry⁴	X		X	X	
Coagulation⁵	X		X	X	
Pregnancy Test (HCG)⁶	X		X	X	
Hepatitis (If Required)^{7,8}	X			X	
Everolimus PK Test⁹		X			
Disease Assessment & Outcomes					
Imaging (MRI)¹¹	X		X*¹¹	X	
Lumbar Puncture (optional)¹²	X		X	X	
Survival Follow Up & Other Treatment					X¹⁵

- 1 Central review of pathology/MRI should be completed concurrently with registration, but is not required before starting therapy.
- 2 If pulse oximetry is less than 93% on room air patient should get a CXR monthly until pulse oximetry is >93%.
- 3 Including CBC with differential
- 4 Including alkaline phosphatase, ALT, AST, total bilirubin, calcium, phosphorus, BUN, creatinine, total protein, albumin, glucose, potassium, sodium, chloride, bicarbonate, uric acid, LDH, and lipid panel (LDL, total cholesterol, triglycerides)
- 5 Including PT/PTT/INR
- 6 For females of child bearing potential, urine or serum pregnancy test as per your institutional guidelines. See Section 3.1.12 for further details.
- 7 Including HBsAg, HBsAb, HBcAb, Hep C RNA. See Protocol Section 3.2.14 for details.
- 8 Patients who test positive for hepatitis B antibodies without receiving prior vaccination will be monitored for HBsAg every 4 weeks.
- 9 PK testing should also be performed 2 weeks post any Everolimus dose adjustment or any CYP3A4 concomitant medication administration/dose adjustment. See Protocol Section 5.2.4 for details.
- 10 Courses are 28 days in length. Each subsequent course following course 1 should begin within 7 days of the end of the prior course.
- 11 MRI of the brain and spine will be performed at the beginning of courses 3, 5, 7, 9, 11, 13, 16, 19, 22, and at the end of treatment visit (after course 24). This assessment should be performed on day 1 of these courses as possible, but may be performed up to 7 days prior to starting these courses if necessary.
- 12 Lumbar puncture for cytology is optional but may be performed if clinically indicated.
- 13 The End of Treatment Visit should be completed within 30 days of treatment termination.
- 14 Adverse event and concomitant medication monitoring should be continued for at least 30 days following the last dose of study treatment
- 15 Survival follow up will be completed by phone or medical record review.

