3.2 Exclusion Criteria

- 3.2.1 Known intolerance or hypersensitivity to Everolimus or other rapamycin analogs (e.g. sirolimus, temsirolimus).
- 3.2.2 Concomitant use of medications known to have strong inhibition or induction of CYP3A enzymes is discouraged and should be discussed with the study PI (see Table 4-7 and 4-8 for a list of prohibited medications). Note that systemic corticosteroids (e.g., dexamethasone is a CYP3A inducer) are not allowed. Inhaled corticosteroids are allowed.
- 3.2.3 Known impairment of gastrointestinal (GI) function or GI disease that may significantly alter the absorption of oral Everolimus.
- 3.2.4 Uncontrolled diabetes mellitus as defined by HbA1c > 8% despite adequate therapy. Patients with a known history of impaired fasting glucose or diabetes mellitus (DM) may be included, however blood glucose and antidiabetic treatment must be monitored closely throughout the trial and adjusted as necessary per standard of care.

3.2.5 Patients who have any severe and/or uncontrolled medical conditions such as:

- 3.2.5.1 Unstable angina pectoris, symptomatic congestive heart failure, myocardial infarction ≤6 months prior to start of Everolimus
- 3.2.5.2 Serious uncontrolled cardiac arrhythmia, or any other clinically significant cardiac disease.
- 3.2.5.3 Symptomatic congestive heart failure of New York Heart Association Class III or IV
- 3.2.5.4 Active (acute or chronic) or uncontrolled severe infection,
- 3.2.5.5 Liver disease such as cirrhosis, decompensated liver disease, and chronic hepatitis
- 3.2.5.6 Known severely impaired lung function (spirometry and DLCO 50% or less of normal and O₂ saturation 88% or less at rest on room air)
- 3.2.5.7 Active bleeding diathesis

3.2.6 Known history of HIV sero-positivity.

3.2.7 Patients who have received live attenuated vaccines within 1 week of start of everolimus and during the study. Patient should also avoid close contact with others who have received live attenuated vaccines. Examples of live attenuated vaccines include intranasal influenza, measles, mumps, rubella, oral polio, BCG, yellow fever, varicella and TY21a typhoid vaccines.

3.2.8 Patients who have a history of another primary malignancy, with the exceptions of: non-melanoma skin cancer, and carcinoma in situ of the cervix, uteri, or breast from which the patient has been disease free for ≥3 years.

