4.5.9 Management of hepatitis reactivation / flare

Reactivation of Hepatitis B (HBV) has been observed in patients with cancer receiving chemotherapy.³² Sporadic cases of Hepatitis B reactivation have also been seen in this setting with everolimus. Use of antivirals during anti-cancer therapy has been shown to reduce the risk of Hepatitis B virus reactivation and associated morbidity and mortality.³³ A detailed assessment of Hepatitis B/C medical history and risk factors must be done for all patients at screening, with testing performed prior to the first dose of everolimus.

4.5.10 Monitoring and prophylactic treatment for hepatitis B reactivation.

Table 4-4 provides details for monitoring and prophylactic therapy according to the screening results of viral load and serologic markers testing.

Table 4-4 Action to be taken based on screening hepatitis B results

Test	Result	Result	Result	Result	Result
HBV-DNA	+	+ or -	-	-	-
HBsAg	+ or -	+	-	-	-
HBsAb	+ or -	+ or -	+ and no prior HBV vaccination	+ or -	- or + with prior HBV vaccination
HBcAb	+ or -	+ or -	+ or -	+	-
Recommendation	Prophylaxis treatment should be started 1-2 weeks prior to first dose of Everolimus Monitor HBV-DNA approximately every 4-8 weeks		No prophylaxis Monitor HBV-DNA approximately every 3-4 weeks		No specific action

Antiviral prophylaxis therapy should continue for at least 4 weeks after last dose of Everolimus. For HBV reactivation definition and management guidelines, see Table 4-5.

Table 4-5 Guidelines for the management of hepatitis B reactivation

HBV reactivation (with or without clinical signs and symptoms)*	
For patients with baseline results: Positive HBV-DNA OR positive HBsAg ----- reactivation is defined as: [Increase of 1 log in HBV-DNA relative to baseline HBV-DNA value OR new appearance of measurable HBV-DNA]	Treat: Start a second antiviral medication AND Interrupt Everolimus administration until resolution: • \leq baseline HBV-DNA levels If resolution occurs within \leq 28 days, Everolimus should be re-started at one dose lower, if available. If the patient is already receiving the lowest dose of Everolimus according to the protocol, the patient should restart at the same dose after resolution. Both antiviral therapies should continue at least 4 weeks after last dose of Everolimus. If resolution occurs $>$ 28 days Patients should discontinue Everolimus but continue both antiviral therapies at least 4 weeks after last dose of Everolimus.

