For patients with baseline results: Negative HBV-DNA and HBsAg AND [Positive HBsAb (with no prior history of vaccination against HBV), OR positive HBcAb] ----- Reactivation is defined as: New appearance of measurable HBV-DNA	Treat : Start first antiviral medication AND Interrupt Everolimus administration until resolution: • \leq undetectable (negative) HBV-DNA levels If resolution occurs within \leq 28 days, Everolimus should be re-started at one dose lower, if available . If the patient is already receiving the lowest dose of Everolimus according to the protocol, the patient should restart at the same dose after resolution. Antiviral therapy should continue at least 4 weeks after last dose of Everolimus. If resolution occurs $>$ 28 days Patients should discontinue Everolimus but continue antiviral therapy at least 4 weeks after last dose of Everolimus.

* All reactivations of HBV are to be recorded as grade 3 (e.g. CTCAE Version 4.03 - Investigations/Other: Viral Reactivation), unless considered life threatening by the investigator, in which case they should be recorded as grade 4. Date of viral reactivation is the date on which the rise or reappearance of HBV-DNA was recorded.

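### The schedule monitors hepatitis B on treatment with HBsAg, but the protocol's monitoring and reactivation rules use HBV-DNA

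*Combined protocol and SAP*

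**What the plan says.** Three parts of the protocol deal with hepatitis B during treatment.

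- **Appendix II (Time and Events Table).** The hepatitis row is marked at Screening and at End of Treatment, with nothing under Courses 2-24. Footnote 8 adds the one on-treatment rule: "Patients who test positive for hepatitis B antibodies without receiving prior vaccination will be monitored for HBsAg every 4 weeks". Footnote 7 lists the panel: "Including HBsAg, HBsAb, HBcAb, Hep C RNA. See Protocol Section 3.2.14 for details". HBV-DNA is not in it. The monthly procedures in Section 5.2.1 contain no hepatitis test.
- **Section 4.5.10, Table 4-4.** Patients positive for HBV-DNA or HBsAg receive prophylaxis and "Monitor HBV-DNA approximately every 4-8 weeks". Patients negative for both, but HBsAb positive without prior vaccination or HBcAb positive, have the entry "No prophylaxis Monitor HBV-DNA approximately every 3-4 weeks".
- **Table 4-5.** It sets out the same two groups. The second is identified by "Positive HBsAb (with no prior history of vaccination against HBV), OR positive HBcAb", and its reactivation criterion is "New appearance of measurable HBV-DNA". The first group's criterion is also an HBV-DNA criterion (a 1-log rise or new appearance). The table's footnote dates reactivation by HBV-DNA.

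Section 3.2.14 requires HBV-DNA as well as serology before everolimus starts in at-risk patients. Section 5.1.12, which implements it, lists serology and hepatitis C RNA but not HBV-DNA.

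For hepatitis C, Table 4-1 has one row covering HBV reactivation and HCV flare that refers to Table 4-5, and a footnote that sends confirmed HCV flare to Table 4-4. The HCV flare instruction, to stop everolimus, is in Table 4-6.

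**The concern.** The schedule and the management tables name different tests for overlapping patients, and no text says which prevails. Section 4.7 has toxicity assessed according to the Time and Events Table, so a site has good reason to work from it.

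The difference matters because HBsAg plays no part in Table 4-5 after baseline; it only sorts patients into groups. A site that followed footnote 8 alone would hold no result able to meet, or date, the reactivation definition. That definition triggers antiviral treatment, interruption of everolimus and an adverse event recorded as at least grade 3. The patients most exposed are those for whom Table 4-4 recommends no prophylaxis, because monitoring is their only specific protection. Sections 4.5.3 and 4.5.9 acknowledge hepatitis B reactivation with everolimus.

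The hepatitis C references are a smaller matter of the same kind: they lead to tables with no HCV instruction.

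**Working it through.** There is no planned figure to reproduce. The check compares the rules and then counts which patients each one reaches.

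**1. The rules side by side**

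| Baseline group | Table 4-4 test and interval | Table 4-5 reactivation criterion | Appendix II, on treatment |
|---|---|---|---|
| (a) HBV-DNA or HBsAg positive | HBV-DNA, about every 4-8 weeks | HBV-DNA only | Nothing for the group as such; HBsAg every 4 weeks if antibody positive and unvaccinated |
| (b) Both negative; HBsAb positive without vaccination, or HBcAb positive | HBV-DNA, about every 3-4 weeks | HBV-DNA only | HBsAg every 4 weeks, if unvaccinated |

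In group (b) the interval is compatible, since 4 weeks lies within 3-4 weeks. The conflict is over the test.

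**2. Tests per 28-day course implied by Table 4-4**

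- Group (b): 28/28 = 1.0 to 28/21 = 1.33 HBV-DNA tests.
- Group (a): 28/56 = 0.5 to 28/28 = 1.0 HBV-DNA tests.
- Appendix II names 0 HBV-DNA tests for either group.

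Rates are per course because treatment stops at progression (Section 4.8), so total exposure varies by patient.

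**3. Which patients footnote 8 reaches**

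Take HBV-DNA, HBsAg, HBsAb, HBcAb and prior vaccination as yes/no: 2^5 = 32 profiles.

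- Group (a): 3 of the 4 HBV-DNA/HBsAg combinations × 8 = 24.
- Both negative leaves 8. HBcAb positive gives 4; HBsAb positive, HBcAb negative and unvaccinated gives 1. Group (b) = 4 + 1 = 5.
- No specific action: 8 - 5 = 3.
- Total: 24 + 5 + 3 = 32, with no profile in two groups.

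Footnote 8 covers patients who are antibody positive (3 of the 4 HBsAb/HBcAb combinations) and unvaccinated. That is 3 × 3 = 9 of the 24 in group (a) and 3 of the 5 in group (b). The 2 missed in group (b) are HBcAb positive and vaccinated, with HBsAb either way. Tables 4-4 and 4-5 attach the vaccination condition to HBsAb only.

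These counts describe what the rule covers. They say nothing about how often each profile occurs.

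**4. Screening**

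Every Table 4-4 column leading to no prophylaxis or no specific action requires a negative HBV-DNA. The panel in footnote 7 and Section 5.1.12 cannot by itself place an HBsAg-negative patient in the right column.

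**5. Hepatitis C references**

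Tables 4-4 and 4-5 both concern hepatitis B. The Table 4-1 footnote is attached to the grade 3 and grade 4 AST/ALT rows, whose default action allows a restart after sufficiently prompt resolution. Its purpose is to override that default. Table 4-6, the correct destination, says to stop everolimus.

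**The case against.** The strongest reply is that the right instruction is already in the protocol. Section 4.5.10 is devoted to hepatitis B monitoring, and Table 4-4 gives test and interval by group. Footnote 7 refers to Section 3.2.14, which names HBV-DNA, and Section 10.6 requires conduct exactly as the protocol describes. Footnote 8 does not say that HBsAg replaces HBV-DNA, so a site could do both. This stands in part: harm requires a site to follow the schedule without Table 4-4. But the schedule states a specific rule of its own, Section 4.7 relies on that schedule, and nothing ranks the two.

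Monthly ALT, AST and bilirubin offer some protection. They are not the Table 4-5 criterion, which applies with or without clinical signs, and Table 4-1 keeps the dose unchanged for grade 1-2 transaminase rises.

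Few patients are likely to be affected. Enrolment is 18, aged 2 to 21, and testing is limited to risk groups or investigator discretion. The exclusion of "Liver disease such as cirrhosis, decompensated liver disease, and chronic hepatitis" may remove some HBV-DNA or HBsAg positive patients. It does not clearly remove those negative for both, who are the main concern. This argument limits the size of the problem and stands.

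Nothing shows whether the 4-weekly HBsAg test was a slip or a deliberate addition. If deliberate, it could be kept alongside HBV-DNA. It cannot serve in its place.

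The hepatitis C references are minor. Section 4.5.11 points correctly to Table 4-6, which follows directly, and Section 4.5.2 lists it.

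**Conclusion.** The concern holds. Footnote 8 names a test that cannot detect reactivation as Table 4-5 defines it, and it omits HBcAb-positive vaccinated patients, whom Tables 4-4 and 4-5 include. The gap is the whole of the HBV-DNA monitoring in the schedule: none named, against about 1.0 to 1.3 tests per course in group (b) and 0.5 to 1.0 in group (a).

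The practical risk rests on a site following the schedule in preference to Table 4-4. The number of patients exposed is unknown because the documents give no prevalence, and it may be zero. Response assessment, error rates and sample size are unaffected. It should be corrected as a safety-monitoring inconsistency; it does not call the design into question. The hepatitis C references are a housekeeping correction and add little to its weight.

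**What to change.** - **Appendix II, footnote 8.** Reword to follow Table 4-4 without overlap: (a) HBV-DNA or HBsAg positive: HBV-DNA about every 4-8 weeks; (b) both negative, with HBsAb positive and no prior vaccination, or HBcAb positive regardless of vaccination: HBV-DNA about every 3-4 weeks. This replaces the 4-weekly HBsAg test. Add a pointer to the hepatitis C monitoring every 4-8 weeks in Section 4.5.11, which the schedule also does not show.
- **Section 5.1.12 and footnote 7.** Name HBV-DNA, in footnote 7 for the screening visit only. Leave the end-of-treatment panel in Section 5.2.3 as it is.
- **Table 4-1.** Keep Table 4-5 for HBV reactivation and send HCV flare to Table 4-6 in both the row and the footnote.

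The cost is a wording amendment. HBV-DNA is named only where Section 3.2.14 or Table 4-4 already asks for it, and no end-of-treatment test is added.
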